- c. Justification and safety information if non-FDA approved drugs without an IND will be administered.

7. Study Statistics

- a. Primary outcome variables:

The study has two co-primary endpoints: (1) the mean Area under the Curve (AUC) of visual analog scale (VAS) pain intensity scores from 0 to 48 hours postoperatively and (2) total opioid consumption (IV morphine equivalents, mg) from 0 to 48 hours postoperatively. The primary hypothesis will be assessed in joint hypothesis testing which controls the type I error at 0.025 across both non-inferiority tests; AUC for VAS pain scores and total opioid consumption through 48 hours postoperatively. Significance will need to be achieved for both co-primary endpoints.

For analyzing the AUC of the VAS pain assessment, we will use an approach that has been previously used in Pacira studies. The area under the curve (AUC) is derived using the trapezoidal rule (see formula below) using the adjusted and imputed VAS pain scores. The VAS scores will be adjusted for the use of rescue medication using the WWOCF approach. AUC will start with the first postsurgical pain assessment. All pain assessments through 48 hours after surgery, including both scheduled and unscheduled will be used in deriving AUC. Exact assessment times will be used in deriving AUC.

$$AUC = \left\{ \sum_{i=2}^n (p_i + p_{(i-1)})(t_i + t_{(i-1)}) \right\} / 2$$

The AUC for VAS may be analyzed using ANOVA with treatment group as a main effect and include other covariates as deemed reasonable. Based on the model, the LS Mean and SE will be reported for each treatment group. The 95% confidence interval for the difference between

treatment groups and the one-sided test performed at 2.5% level of significance will be inspected for non-inferiority.

Total opioid consumption over 48 hours postoperatively will be abstracted by our research assistant from the medical administration record (MAR) as it appears in the EMR for each patient.

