The analysis of total opioid consumption over 48 hours is based on an approach that has been used previously in Pacira studies. For the endpoint total opioid consumption (IV morphine equivalents, mg) from 0 to 48 hours postoperatively, opioid dose will be converted to IV morphine equivalent dose using the conversion factor from the table below. The endpoint will be the summation of all opioids taken post-surgery through 48 hours. Subjects with no opioid use during the period in question will be assigned a dose of 0 mg for summaries.

The total opioid consumption through 48 may be analyzed using ANCOVA with treatment group as a main effect and include other covariates as deemed reasonable. Based on the model, the LS Mean and SE will be reported for each treatment group. The 95% confidence interval for the difference between treatment groups and the one-sided test performed at 2.5% level of significance will be inspected for non-inferiority. The data may be natural log transformed.

Medication	Unit	Route	IV Morphine Conversion Factor
Duramorph	mcg	IT	0.1
Oxycodone, Oxycocet, Percocet, acetaminophen-oxycodone	mg	PO	0.5
Morphine	mg	IV, IM, SC	1
Morphine	mg	PO	0.33
Hydromorphone (Dilaudid)	mg	IV, IM, SC	6.67
Hydromorphone (Dilaudid)	mg	PO	1.3
Fentanyl	mg	IV, PO, IM	100
Hydrocodone combination product - Vicodin, Norco, Lorcet, Lortab, hydrocodone-acetaminophen, Ketobemidone	mg	PO	0.33
Codeine combination product - Tylenol 3, acetaminophen-coedine, Paracetamol Forte, Tylenol 4	mg	PO	0.05
Ultram, Tramadol, Tramadol hydrochloride	mg	PO, IM	0.08
Demerol, Meperidine, Pethidine	mg	IV, SC	0.1
Demerol, Meperidine, Pethidine	mg	PO	0.033
Ketobemidone, Oxycodone	mg	IV	1

Regarding the non-inferiority margin for the total opioid endpoint, previous literature indicated a difference of 10.6mg IV morphine equivalent dose daily is a clinical different threshold [24]. Therefore, total opioid consumption through 48 hours for LB treatment group is to be no more than 21.2 IV (10.6 x 2 Days) morphine equivalent doses greater than the total opioid consumption through 48 for TEA treatment group. It may be reasonable to apply a natural log transformation, in which case the NIM threshold will be adjusted accordingly.

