The study is powered for the primary outcome of Area under the Curve (AUC) for pain from 0-48 hours. From review of the literature of previous studies, we deemed a margin of 80% of 48 hours to be non-inferior [24,25,]. A group sample size of 50 per cohort is needed achieve a 90% power to detect non-inferiority using a one-sided, Mann-Whitney test. The margin of non-inferiority is 38 (80% of 48 hours). The non-inferiority margin corresponds to an increase in pain, not a decrease. The pain VAS ranges from 0 to 10, with 10 being the worst pain. Therefore, non-inferiority will be declared if the average AUC for liposomal bupivacaine is no more than 38 units compared to the average AUC in the TEA group. The true difference between the means is assumed to be 0.0. The significance level (alpha) of the test is 0.025 and the data are drawn from populations with standard deviations of 55.0. These assumptions were derived from previous Pacira studies. It is reasonable to assume that the standard deviation of the AUC for 0-48 hours is about 55 units and the difference between the groups is 0. Sample size calculations were performed using PASS (PASS 16 Power Analysis and Sample Size Software (2018). NCSS, LLC. Kaysville, Utah, USA, ncss.com/software/pass). Of note, with sequential testing of the co-primary endpoints, the study remains to be adequately powered with the addition of the total opioid consumption co-primary endpoint. A sample size of 50 participants in each arm will have adequate power (>90%) to detect non-inferiority with a margin of 21.2 IV morphine equivalents using a one-sided test with a common standard deviation of 25 and alpha of 0.025. The non-inferiority margin was determined by the clinically significant threshold of 10.6 mg in daily IV morphine equivalent dose [24], therefore, 21.2 morphine equivalent dose for over 2 days (0-48 hours).

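### Section 7a's sentence on when non-inferiority is declared reads as a point-estimate rule, which conflicts with the plan's own one-sided 2.5% test and both-endpoints requirement

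*Combined protocol and SAP*

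**What the plan says.** All the relevant text is in section 7a (Study Statistics, Primary outcome variables) of the combined protocol and SAP.

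- **Opening paragraph.** Joint testing is to hold the type I error at 0.025 over the two non-inferiority tests, and "Significance will need to be achieved for both co-primary endpoints".
- **AUC analysis paragraph.** The 95% confidence interval for the difference between "treatment groups and the one-sided test performed at 2.5% level of significance will be inspected for non-inferiority". It does not say which limit is compared with which value.
- **Opioid paragraphs.** The analysis paragraph repeats the confidence interval and the one-sided 2.5% test. The later paragraph on the margin says that "total opioid consumption through 48 hours for LB treatment group is to be no more than 21.2 IV (10.6 x 2 Days) morphine equivalent doses" above the TEA group. It allows a log transformation with an adjusted margin.
- **Sample-size paragraph.** "A group sample size of 50 per cohort is needed achieve a 90% power to detect non-inferiority using a one-sided, Mann-Whitney test". It adds that "The significance level (alpha) of the test is 0.025 and the data are drawn from populations with standard deviations of 55.0". Between these two statements it says that "non-inferiority will be declared if the average AUC for liposomal bupivacaine is no more than 38 units compared to the average AUC in the TEA" arm. This is the only sentence in the plan that uses the word declared for the primary conclusion. It mentions neither a confidence limit nor a test result, and it leaves out the opioid endpoint.

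**The concern.** A non-inferiority test asks whether the data rule out a difference as large as the margin. A rule that only asks whether the observed averages differ by no more than the margin does not ask this: the interval around such a result can extend well past the margin. The sample-size paragraph therefore contains a declaration sentence and an alpha that cannot both hold for the same comparison.

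What is at stake is how a borderline result is handled. A range of observed AUC differences would pass the declaration sentence and fail the 2.5% test. In an unblinded trial, the primary conclusion should not depend on which sentence of section 7a the analyst follows. The sentence taken alone would also allow a declaration on AUC without regard to opioid consumption, contrary to the opening paragraph of the section.

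**Working it through.** **Inputs (section 7a, sample-size paragraph):** AUC margin 38 (0.80 × 48 = 38.4, given as 38); SD 55 in each group; 50 per arm; assumed true difference 0; one-sided alpha 0.025; target power 90%. For opioids: margin 21.2 mg, SD 25, alpha 0.025.

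**1. Reproduce the stated sample size under the 2.5% test.** n per arm = 2 × 55² × (1.960 + 1.282)² / 38² ≈ 44.0, rounded up to 45. Dividing by the Mann-Whitney efficiency for normal data, 3/π = 0.955, gives 45 / 0.955 = 47.1, rounded up to 48. This is within 2 of the stated 50. At 50 per arm, power is 92.8% (t-test) or 91.6% (Mann-Whitney). The plan's figure is consistent with a one-sided 2.5% test.

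**2. Standard error of the AUC difference.** SE = 55 × √(2/50) = 11.0.

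**3. Largest observed difference (LB minus TEA) that passes.**
- Literal sentence: 38.
- Upper 95% limit below 38, t-based with 98 degrees of freedom: 38 − 1.984 × 11.0 = 16.2. With the normal quantile: 38 − 1.960 × 11.0 = 16.4.

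Observed differences between about 16.2 and 38 get opposite answers.

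**4. Probability that the AUC component passes (normal approximation).** Literal sentence: Φ((38 − d)/11.0). Confidence-limit rule: Φ((16.44 − d)/11.0).

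| True difference d | Literal sentence | 95% limit below 38 |
|---|---|---|
| 0 | 99.97% | 93.2% |
| 38 (the margin) | 50.0% | 2.5% |
| 45 | 26.2% | 0.5% |
| 50 | 13.8% | 0.1% |

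In 200,000 simulated trials at d = 38, the literal rule passed 49.7% of the time and the t-based confidence-limit rule 2.45%. The literal rule's error falls to 2.5% only at d = 38 + 1.960 × 11.0 = 59.6.

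**5. Which rule was the design based on?** The literal rule would pass 99.97% of the time at a true difference of 0. The plan states 90%, which matches the 2.5% test in step 1.

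**6. Does the opioid endpoint contain the error?** Not by itself. If opioid use is truly equal, the 2.5% opioid test has 98.7% power at 50 per arm. Assuming independence, the chance of overall success with AUC at its margin under the literal rule is 0.50 × 0.987 = 49%.

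**The case against.** The strongest reply is that section 7a, read as a whole, already contains the inferential rule. The opening paragraph requires significance on both endpoints, in mandatory language. The analysis paragraphs give the 95% interval and the one-sided 2.5% test for AUC and for opioids. The sample-size paragraph itself names a one-sided test before the disputed sentence and the alpha after it. That sentence follows a remark that the margin concerns an increase in pain, so it may have been meant only to show direction or to state the alternative hypothesis for population means. Each endpoint has one margin in one direction, so the upper limit can be inferred as the relevant one.

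Most of this stands, and it rules out three stronger readings that a reader might infer:

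- *The trial was designed with a 50% false-positive rate.* The documents do not support this. The sample size fits alpha 0.025. The 50% is a general property of comparing any estimate that is symmetric about the true value with a margin, whatever the SD or n.
- *The plan has no inferential criterion.* It has one, but it is spread over several paragraphs.
- *The opioid endpoint has the same defect.* The sentence with 21.2 opens as a statement about the margin, does not speak of declaring anything, and follows a paragraph that gives the interval and the test.

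What does not fall away is that the one sentence about declaring non-inferiority states a criterion different from the test. The text that would correct it says only that the interval and test will be inspected. A reader can work out the intended rule, but the plan for a primary conclusion should state it.

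**Conclusion.** The declaration sentence is wrong as written and should be corrected before analysis. It is a wording error in the decision rule: the stated alpha, the named one-sided test, the both-endpoints requirement and the reproduced sample size all point to the 2.5% test as the intended rule.

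If the sentence were followed literally, the AUC cut-off for the observed difference would be 38 instead of about 16.2, and the AUC component would pass 50% of the time at the margin instead of 2.5%. The 16.2 rests on SD 55, 50 per arm and a t-based analysis; the plan has not fixed that analysis, since ANOVA is optional and the power calculation uses Mann-Whitney. The 50% needs only an estimator symmetric about the true difference. Both figures describe AUC alone.

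**What to change.** Replace the declaration sentence in the sample-size paragraph with:

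> Non-inferiority will be declared only if, for both co-primary endpoints, the one-sided 2.5% test against the margin is significant, i.e. the upper limit of the two-sided 95% CI for LB minus TEA from the primary analysis is below 38 for AUC0-48 and below 21.2 mg (or the corresponding pre-specified margin if the log scale is used) for 0-48 h opioid consumption.

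In the opioid margin paragraph, add a cross-reference to this rule.

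The wording refers to the primary analysis on purpose. It does not choose between ANOVA and Mann-Whitney for AUC, or decide on the log transformation for opioids. The sponsor's statistician still has to settle those choices separately and in advance.

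The cost is one replaced sentence and one cross-reference. No extra patients or data are needed. The 50 per arm already assumes one-sided 0.025, and AUC power stays at 92.8% (t-test) or 91.6% (Mann-Whitney) under the plan's assumptions.

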5. Length of hospital stay and time (in days) to meeting discharge criteria. Often, patients remain inpatient beyond the time at which they first meet discharge criteria due to a variety of psychosocial factors. Thus, length of hospital stay and time (in days) to meeting discharge criteria will be separately recorded. Discharge eligible criteria include: (1) hemodynamically stable, (2) afebrile, (3) ROBF, (4) pain controlled with oral analgesics, (5) independence with ADLs, (6) walking greater than 250 feet.

6. Total intravenous fluids administered and time to postoperative diuresis defined as the time lapse from date of surgery (DOS) to a net negative fluid balance sustained over a 24 h time period.

7. Need for vasopressors (amount and duration).

8. Incidence of major postoperative complications, including 30-day hospital readmission.

9. Total direct costs associated with loco-regional anesthesia: The analysis will include the direct variable cost of supplies and pharmacy (including initiation of PCA in the event of block failure) as well as anesthesia professional fees (TEA only; both intraop and postop) and cost of OR time in minutes to perform the blocks.

10. Post-discharge narcotic utilization. Total outpatient narcotic use during the immediate outpatient postoperative period will be obtained from the patient by nurse phone survey on postoperative day 14, provided the patient is outpatient and not still admitted or readmitted to the hospital.

Translational Endpoints:

1. Biomarkers of surgical stress response. Blood samples (10mL of whole blood) will be collected on the DOS when routine IV access is established in preop or the operating room and postoperative days 1 through postoperative day 7 coinciding with routine IV access for blood, for analysis of peripheral blood counts. Blood collection on postoperative day 0 is optional. Serum will

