Many randomized controlled trials over the past 20 years have focused on the benefits of TEA. TEA is effective in attenuating the surgical stress response and reducing pain and opioid consumption for up to 72 hours (h) following abdominal incisions, and also has an impact on complications following abdominal surgery, reducing the time to bowel recovery by up to 36 h and may reduce cardiac and respiratory complications in high-risk patients.⁶⁻⁸ While analgesia and recovery seem to be better with TEA than intravenous opioid patient controlled analgesia (PCA), the role of TEA in pain control for patients on ERAS programs following open gynecologic and colorectal surgery is controversial. TEA failure rates are as high as 30% and many of these patients will require supplemental opiates.⁹ The sympathetic block that results from TEA commonly results in hypotension that results in at least temporary discontinuation of the infusion, prompts intravenous fluid administration to already volume overloaded patients and may require treatment with vasopressors.¹¹ TEA may hinder achievement of other ERAS goals such as mobilization and removal of urinary catheters, and TEA has been shown to increase length of hospital stay and complication rates in gynecologic cancer surgery.^{12, 13}

Given these disadvantages, some leading ERAS programs use surgical site infiltration with long acting local anesthetics in lieu of TEA. Extended-release liposomal bupivacaine (LB) was recently approved by the FDA for single-dose surgical site infiltration to produce postsurgical analgesia. The liposomal preparation consists of microscopic multi-vesicles with a lipid-soluble lining and an aqueous core containing encapsulated bupivacaine allowing it to be slowly released over a period of up to 72–96 h.¹⁴ Existing data indicate that surgical site infiltration with LB following mastoplasty and open colectomy decreases postoperative opioid requirements and length of stay.^{15, 16} Recently, the Mayo Clinic published their

experience with abdominal incision injection of LB versus standard bupivacaine hydrochloride after laparotomy for gynecologic malignancies. Compared to bupivacaine hydrochloride, abdominal incision infiltration with LB was associated with less opioid consumption as well as lower rates of postoperative nausea and ileus. Pain scores, length of hospital stay and total pharmacy costs did not differ between the groups.¹⁷

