To date, there has never been a comparison between the analgesic efficacy of TEA and LB surgical site infiltration following open abdominal surgery. In many cases, cost and concerns about reimbursement have hindered approval of LB within hospital formularies. These concerns stem from Centers for Medicare and Medicaid Services (CMS) mandated bundling of reimbursement for all drugs used during a surgical procedure with the procedure itself as well as from inconsistencies in contracts between hospitals and private/commercial insurers regarding payment policies for separately payable drugs. However, the cost of TEA significantly exceeds that of LB. The cost of a 20 mL single use vial of LB is less than or equal to the cost of a continuous epidural kit. TEA incurs the added expenses of (a) professional fees for placement and daily management and (b) the use of operating room (OR) time for placement (~\$14 dollars/min at our institution). Currently on the JHH gynecologic oncology ERAS program, 40% of epidurals are placed in the OR with an average OR time expenditure of 30 minutes per epidural. Additional pharmacy costs also accumulate in the 30% of cases of failed TEA.

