"Routine care" is quite varied for laparotomies at our institution, as well as among large volume surgical centers. Thoracic epidural analgesia is standard at some institutions while surgical incision infiltration of bupivacaine or liposomal bupivacaine is the primary modality of pain

control at other institutions. Within the gynecologic oncology division at our institution not all individuals receive an epidural for analgesia based upon surgeon preference therefore this study does not require one arm of patients to receive non-routine care as “standard pain management” has yet to be defined by clinical data.

- e. Justification for inclusion of a placebo or non-treatment group.

Not applicable. Both arms will receive a proven modality of post-operative analgesia.

- f. Definition of treatment failure or participant removal criteria.

If the patient has been randomized to the TEA arm of the trial and an epidural cannot be placed or cannot be used due to other circumstances (ie. persistent hypotension) the patient will receive the other elements of the ERAS multimodal pain bundle, which is consistent with our current clinical practice. Intention to treat statistical analyses will be used to test the null hypothesis.

- g. Description of what happens to participants receiving therapy when study ends or if a participant’s participation in the study ends prematurely.

In the rare event a patient enrolled on trial does not proceed with surgery or decides not to participate in the trial preoperatively, their slot will not be reallocated in the randomization scheme. In the event a participant wishes to drop out of the study prematurely postoperatively (ie. declines further blood/saliva collection and/or to fill out surveys), they will be allowed to do so and the data collected during their enrollment period will still be used for analyses unless they submit a formal written objection.

5. Inclusion/Exclusion Criteria

Inclusion:

- Individuals ≥ 18 years of age
- Planned laparotomy by and admitted to the gynecologic oncology service at JHH.

Exclusion:

- Individuals who have a contraindication to thoracic epidural analgesia
 - o Individuals with a coagulation disorder
 - o Individuals with an infection at the site of epidural placement
 - o Individuals with intracranial pathology such as non-communicating increased intracranial pressure or obstruction of cerebrospinal fluid flow related to mass lesions

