Intention to treat statistical analyses will be used to test the null hypothesis. Thus, if a patient has been randomized to the TEA arm of the trial and an epidural cannot be placed or cannot be used due to other circumstances (ie. persistent hypotension) the patient will receive the other elements of the ERAS multimodal pain bundle, which is consistent with our current clinical practice and that patient's data will be included in the dataset for the TEA arm in the final analysis. Additionally, in the event a participant wishes to drop out of the study prematurely postoperatively (ie. declines further blood/saliva collection and/or to fill out surveys), they will be allowed to do so and the data collected during their enrollment period will still be included in the dataset for their respective treatment arm unless they submit a formal written objection.

Secondary outcome variables:

T-tests or the nonparametric Mann-Whitney test will be used to compare normally and non-normally distributed data between the study arms. The log-rank test will be used to compare the time to (ROBF) as well as the time to postoperative diuresis to account for right censoring in which case no event (ROBF/diuresis) is observed within the observed time. A Poisson regression model will be used to compare the length of hospital stay. Chi-square tests will be used to compare the incidence of major postoperative complications between the two treatments. Chi-square tests will also be used to compare the incidence of major postoperative complications between the two treatments. Daily mean and median as well as mean baseline change in surgical stress biomarkers will be compared between treatment groups using t-tests or the Mann-Whitney test depending on whether data are normally or non-normally distributed. Average daily QoR-15 scores will be compared between the study cohorts.

b. Early stopping rules.

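### Intention-to-treat is the only analysis set, so with up to 30% epidural failure a pass supports non-inferiority to intended TEA, not to a working epidural

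*Combined protocol and SAP*

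**What the plan says.** Section 4f and Section 7a of the combined protocol and SAP both state: "Intention to treat statistical analyses will be used to test the null hypothesis". If an epidural cannot be placed or used in a TEA patient (persistent hypotension is the example), "the patient will receive the other elements of the ERAS multimodal pain bundle, which is consistent with our current clinical practice". Section 7a adds that "that patient's data will be included in the dataset for the TEA arm in the final analysis". The document contains no per-protocol or as-treated set and no sensitivity analysis for block failure. The title of Section 4f promises a definition of treatment failure, but for a failed block the text gives only this handling rule.

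The plan expects the event. Section 3 says "TEA failure rates are as high as 30% and many of these patients will require supplemental opiates", as does the opening rationale. The cost argument in Section 3 says "Additional pharmacy costs also accumulate in the 30% of cases of failed TEA". Secondary objective 9 counts supply and pharmacy costs "including initiation of PCA in the event of block failure".

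On the endpoints, Section 7a says of the pain AUC: "The VAS scores will be adjusted for the use of rescue medication using the WWOCF approach". Of the joint test it says: "Significance will need to be achieved for both co-primary endpoints".

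**The concern.** In a superiority trial, diluting one arm usually works against the claim. In a non-inferiority trial it can work in favour of the claim. A TEA patient without a working block who takes more opioid raises the TEA mean on the second co-primary endpoint directly. The same opioid doses can raise the first. Under WWOCF, pain scores within 2 to 6 hours of a rescue dose are replaced by the patient's highest score since the previous rescue window or the end of surgery. Both shifts move the ITT difference in favour of LB.

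What is at stake is how a positive result is read. The objectives speak of non-inferiority to TEA on efficacy endpoints, Section 3 presents the trial as the missing comparison of analgesic efficacy, and the results are meant to inform national guidelines. A reader could take a pass to mean that LB matches a functioning epidural. ITT alone does not show that.

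**Working it through.** **Inputs from Section 7a.** 50 per arm; one-sided alpha 0.025; assumed true difference 0; AUC margin 38 and SD 55; opioid margin 21.2 mg and SD 25. Failure share f is up to 0.30 (Section 3).

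**The plan's own figure.** n = 2 × [55 × (1.960 + 1.282) / 38]² = 44.0, so 45 per arm. The t-based version gives 46. Dividing by the Mann-Whitney efficiency for normal data, 3/π = 0.955, gives 49, against the stated 50. Power at 50 per arm with that efficiency is 91.6%. Opioid power is about 99%. The sample size reproduces; this point is not an arithmetic error in it.

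**Assumption.** Let x be the excess of failed over working TEA. The documents do not give x. The reference case is x = one margin, with LB also exactly one margin worse than a working epidural, so that failed TEA performs like LB. Without failures, the chance of passing each endpoint would be 2.5%.

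**Formula.** ITT difference = margin − f × x. SE = SD × √(2/50), which is 11 for AUC and 5 for opioid. P(pass) ≈ Φ(f × x / SE − 1.96).

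At f = 0.30 and x = margin:
- AUC: the shift is 0.3 × 38 = 11.4, so the difference falls from 38 to 26.6. Φ(11.4/11 − 1.96) = Φ(−0.92) = 17.8%, or 17.5% with the t distribution.
- Opioid: the shift is 0.3 × 21.2 = 6.36, so the difference falls from 21.2 to 14.8. Φ(6.36/5 − 1.96) = Φ(−0.69) = 24.6%, or 24.2% with the t distribution.

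Single-endpoint results (normal approximation):

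| Failure share f | x | AUC | Opioid |
|---|---|---|---|
| 0% | any | 2.5% | 2.5% |
| 10% | 1 margin | 5.3% | 6.2% |
| 20% | 1 margin | 10.2% | 13.3% |
| 30% | 0.5 margin | 7.5% | 9.3% |
| 30% | 1 margin | 17.8% | 24.6% |
| 30% | 1.5 margins | 34% | 48% |

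Adding the extra variance from mixing failed and working epidurals changes the 30%, one-margin row only to 17.1% and 23.2%.

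**Both endpoints required.** In the reference case at 30% failure, with both endpoints at the margin, independence gives 0.178 × 0.246 = 4.4% and perfect correlation gives the smaller value, 17.8%. Without failures the corresponding range is 0.025² = 0.06% to 2.5%.

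**Equivalent statement.** If 30% of TEA patients do no better than LB, the ITT difference reaches the margin only when LB is 38/0.7 = 54.3 AUC units, or 21.2/0.7 = 30.3 mg, worse than a working epidural.

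**Power of a per-protocol comparison.** Removing 30% of TEA patients leaves 50 versus 35. The AUC SE is 55 × √(1/50 + 1/35) = 12.1. With a true difference of 0 in that set, t-based power is about 87% for AUC and 97% for opioid. Suppose instead that the ITT difference is 0 and failed patients have one extra VAS point over 48 hours. The failures then carry 0.3 × 1 × 48 = 14.4 units, LB is 14.4 worse once they are removed, and AUC power falls to about 49%. With two extra points (28.8 units) it is about 11%.

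**The case against.** The strongest reply is that ITT answers the question the plan asks. Section 7a keeps failed epidurals in the TEA arm on purpose and describes their care as current practice. The rationale lists failure among the disadvantages of TEA, and the cost endpoint counts PCA after block failure. On that reading failures belong to the comparator, and the smaller difference is real. This stands: ITT is the right primary analysis for a comparison of strategies. What it leaves open is the claim against a functioning epidural, because the plan never says which of the two claims it will make.

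Three stronger readings are tempting, and the documents do not support them.

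- A reader might infer that ITT is invalid here, or that it makes an inferior LB pass. That holds only if inferior means inferior to a working epidural.
- A reader might infer a much larger error. With one or two extra VAS points in every failed patient for all 48 hours, the AUC pass rate would be 25% or 74%. Those penalties are pure assumption. They make failed TEA 48 or 96 AUC units worse than working TEA, well beyond an LB that is itself 38 worse, and they ignore the second endpoint. Section 3 also describes some hypotension-related stops as possibly temporary.
- A reader might infer that per-protocol success should be required for the primary claim. Exclusion after randomisation would fall mainly on TEA failures, since a single infiltration can hardly be stopped. The comparison could therefore be biased against LB.

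Nor are failures invisible in the data. PCA started for block failure enters the cost analysis, so many should be identifiable. What is missing is a definition and a planned use of that information.

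**Conclusion.** The point holds in a limited form. As planned, a positive result would support non-inferiority of LB to a strategy of intended TEA, but could not be attributed to LB matching a functioning epidural. ITT is not conservative for that second claim.

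The direction follows from the plan's own statements on failure and supplemental opiates. The size is an illustration: in the reference case the nominal 2.5% becomes roughly two to ten times as large on a single endpoint as failure goes from 10% to 30%. Requiring both endpoints limits the error without removing it. These figures rest on three things the documents do not settle: the failure rate in this trial (30% is an upper figure), the outcome level in failed TEA (only extra opiate need is stated; higher pain is inferred), and the correlation between endpoints. This should be repaired before analysis, but it does not undermine the primary test.

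**What to change.** 1. Keep ITT as the primary analysis in Section 7a, and state that it compares LB with a strategy of intended TEA.
2. Define block failure in advance for analysis purposes only, using data already recorded.
3. Add a pre-specified supportive per-protocol analysis (assigned block delivered and used as planned), with the same model and the same margins of 38 and 21.2.
4. Report the TEA failure rate beside the primary result.
5. If the per-protocol result does not agree with ITT, word the conclusion as non-inferior to a strategy of intended TEA.

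The cost is one definition and one further analysis set, with no added patients. The downside is that the per-protocol comparison is not fully randomised and can be biased against LB. With 35 TEA patients its AUC power is about 87% only if the true difference without failures is 0, and lower otherwise. It should therefore support the primary claim and not gate it.
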